11.7 Anticipated or Unanticipated

If an AE is determined to be related to the study device the sponsor will then assess the event to determine if it is anticipated or unanticipated.

- **Anticipated:** the event is identified in the CIP; labeling; report of priors or user guide.
- **Unanticipated:** the event has not been previously identified in the CIP; labeling; report of priors or user guide.

12. Data Review Committees

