9.9 Study Stopping Rules

The study may be stopped if the Data Monitoring Committee (DMC) determines that there are significant safety issues, including the occurrence of certain types of individual adverse events (i.e. UADE, device related DKA, device related HHS and device related Severe Hypoglycemia) that have undergone expedited adjudication by the Clinical Events Committee (CEC). See CEC **Section 12.1** and DMC **Section 12.2** for more details regarding the expedited review responsibilities of both committees.

10. Risks and Benefits

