
Risks with the use of an insulin infusion pump may include the risk of malfunction of the components of the system (pump, software, infusion set and reservoir) as well as the risk of use error during use of the system. DDs or use errors can result in administration of too much or too little insulin which can lead to the following clinical consequences:
 
 • Hypoglycemia • Hyperglycemia • Diabetic ketoacidosis or HHS • Severe hypoglycemia with or without associated seizure, coma or death • Kinked cannula leading to hyperglycemia • Infusion set disconnection from pump leading to hyperglycemia • Subject removes the reservoir from the pump but forgets to disconnect the infusion set from the body which results in hypoglycemia or severe hypoglycemia • Dislodged cannula leading to hyperglycemia • A pump error may lead to under delivery or over-delivery of insulin • Battery failure – no insulin delivered • Insulin deterioration leading to hyperglycemia • Incomplete priming; fails to prime tubing and/or cannula, leading to hyperglycemia 	
Prevention and mitigation include:
 
 • Follow the provided user guides & instructions for insulin and insulin pump management which includes information on infusion set change. • Train prior to study device use on appropriate device use and diabetes management principles and instruct to call investigator with problems. • Instruct to check their meter glucose if their high or low symptoms do not match their sensor alerts or SG readings in order to make diabetes treatment decisions. • Instruct to check their meter glucose if there are any concerns that the SG value is not accurate. • Instruct to have glucose and glucagon on hand for hypoglycemia. • Instruct to change infusion set if suspected catheter occlusion or administer insulin with syringe for persistent hyperglycemia especially if ketones develop.

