11.2 Definitions and Classification of Adverse Events

Medtronic uses the definitions provided in ISO 14155:2020 and 21 CFR 812 for AE definitions. Where the definition indicates "device", it refers to any device used in the study. This might be the device under investigation, or any market released component of the system.

Severe Hypoglycemia is an event requiring assistance of another person due to altered consciousness to actively administer carbohydrate, glucagon, or other resuscitative actions.^[5]

This means that the subject was impaired cognitively to the point that he/she was unable to treat himself or herself, was unable to verbalize his or her needs, and was incoherent, disoriented and/or combative.

These episodes may be associated with sufficient neuroglycopenia to induce seizure or coma. Plasma glucose measurements may not be available during such an event, but neurological recovery attributable to the restoration of plasma glucose to normal is considered sufficient evidence that the event was induced by a low plasma glucose concentration. ^[5]

Severe Hyperglycemia is defined as hyperglycemia (BG greater than [$>$] 300 mg/dL) with BG ketones greater than ($>$) 1.5 mmol/L, and/or accompanied by symptoms of nausea, vomiting or abdominal pain.

The meter and ketone test strips are supplied for the evaluation of ketone monitoring. Only blood ketones will be recognized (not urine ketones) for assisting in diagnosis of severe hyperglycemia. The monitors/test strips are quality controlled prior to dispensing to subjects. Blood ketones provide contemporaneous understanding of ketone levels associated with elevations in glucose.

Diabetic Ketoacidosis/DKA diagnostic criteria: BG greater than ($>$) 250 mg/dL, arterial pH less than ($<$) 7.3, bicarbonate less than ($<$) 15 mEq/L, moderate ketonuria or ketonemia and requiring treatment within a health care facility.^[6]

Hyperglycemic events will be recorded as DKA if the event includes the presence of all of the following:

- Arterial blood pH less than ($<$) 7.30 or serum bicarbonate less than ($<$) 15 mEq/L
- Blood glucose greater than ($>$) 250 mg/dL
- Serum ketones or large/moderate urine ketones
- Symptoms such as polyuria, polydipsia, nausea, or vomiting
- Treatment provided in a health care facility

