- c) foetal distress, foetal death or a congenital abnormality or birth defect including physical or mental impairment

Note 1 to entry: Planned hospitalization for a pre-existing condition, or a procedure required by the CIP, without serious deterioration in health, is not considered a serious adverse event.

Serious Adverse Device Effect (SADE) (ISO 14155:2020)

Adverse device effect that has resulted in any of the consequences characteristic of a serious adverse event

Unanticipated Adverse Device Effect (UADE) (21 CFR 812.3(s))

Any serious adverse effect on health or safety or any life-threatening problem or death caused by, or associated with, a device, if that effect, problem, or death was not previously identified in nature,

severity, or degree of incidence in the investigational plan or application (including a supplementary plan or application), or any other unanticipated serious problem associated with a device that relates to the rights, safety, or welfare of subjects.

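### Section 11.7 omits the severity and incidence tests of the protocol's own UADE definition, so some serious device-related events that are already named could miss the expedited safety route

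*Protocol*

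**What the plan says.** Section 11.7 applies once an adverse event has been judged device-related: "the sponsor will then assess the event to determine if it is anticipated or unanticipated". An event is anticipated if "the event is identified in the CIP; labeling; report of priors or user guide", and unanticipated if "the event has not been previously identified in the CIP; labeling; report of priors or user guide". The only test is whether the event has been identified. Nothing is said about how severe or how frequent the identified event was expected to be.

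Section 11.2 states that "Medtronic uses the definitions provided in ISO 14155:2020 and 21 CFR 812 for AE definitions" and gives the UADE definition from 21 CFR 812.3(s). Under it, a serious device effect is unanticipated if it was not previously identified in nature, "severity, or degree of incidence in the investigational plan or application".

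UADE status decides routing. Section 9.9 lists the events that receive expedited adjudication as "UADE, device related DKA, device related HHS and device related Severe Hypoglycemia", and sections 12.1 and 12.2 use the same four. Section 11.5 sets a 10-working-day limit for the investigator's UADE report to the sponsor and the IRB.

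**The concern.** Two rules in one protocol answer the same question by different tests. Table 4 in section 10.1 names many harms, among them infection, allergic reaction and cardiovascular event, and attaches no rate to any of them. On a literal reading of section 11.7, being on that list settles the matter, whether the event occurs once or in a cluster and whether it is mild or life-threatening.

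For serious device-related events other than DKA, HHS and severe hypoglycemia, UADE status is the only listed entry to the expedited route. A wrong label could therefore cost the UADE report, the early FDA notice, timed CEC adjudication and the DMC meeting tied to it. Phase 2 introduces the DS5, a new integrated sensor-transmitter with its own inserter, so a change in the severity or frequency of insertion-site harm is a signal the trial should be able to pick up.

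**Working it through.** No sample size, power or event count is involved. The check is a comparison of the texts, followed by simple arithmetic on the review intervals.

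**1. The two rules side by side**

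- Tests applied: section 11.2 uses three (nature, severity, degree of incidence). Section 11.7 uses one (the event is identified). Two of the three are absent.
- Reference sources: section 11.2 looks to the investigational plan or application. Section 11.7 looks to the CIP, labeling, report of priors and user guide.
- Scope: section 11.2 covers serious effects. Section 11.7 covers any device-related adverse event.
- Cross-reference: none in either direction, and no statement of which governs.

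**2. Can they disagree on one event?**

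- *Allergic reaction to the sensor.* Table 4 names it without grading it. If it is life-threatening, section 11.7 gives anticipated. Section 11.2 asks whether that severity had been identified, and could give UADE.
- *Insertion-site infection.* Table 4 names infection, and section 11.3 uses hospitalized cellulitis at a device insertion site as its example of a SADE. The CIP thus covers nature and that level of severity. A run of such cases above any previously identified incidence could be a UADE under section 11.2, but is anticipated under section 11.7.
- *Serious device-related severe hyperglycemia.* It is defined in section 11.2 and used as a causality example in section 11.6, so it is identified in the CIP. The CEC reviews it under section 12.1, but it is not on the expedited list.
- *A harm for which the rules do not affect expedited review.* Table 4 also lists "Severe hypoglycemia with or without associated seizure, coma or death". Device-related severe hypoglycemia is expedited whatever label section 11.7 gives it.

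**3. What hangs on the label**

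Of the four expedited triggers, one (UADE) can be affected and three (device-related DKA, HHS and severe hypoglycemia) cannot. For an event whose only possible trigger is UADE, the steps at risk are:

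- the investigator's report within 10 working days (section 11.5);
- FDA notice in about 3 business days (section 12.2);
- CEC adjudication within 10 business days of sponsor notification (section 12.1);
- a DMC meeting within 10 business days of adjudication (section 12.2).

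**4. Timing of DMC review**

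- Expedited, nominal: 10 + 10 = 20 business days, which is 20 / 5 = 4 weeks, or about 28 days. Section 12.1 allows final disposition to be delayed while information is obtained, so this is not guaranteed.
- Routine: the DMC meets about every 90 days, so the wait is 0 to 90 days. If events fall at random between meetings, the average is 90 / 2 = 45 days.
- Difference: about 45 − 28 = 17 days on average and 90 − 28 = 62 days at worst. The longest routine wait is about as long as one subject's 90-day SmartGuard period.

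**The case against.** A reader might infer that section 11.7 has replaced the UADE definition, so that worse or more frequent device harms never reach expedited review and hardly any serious event could be a UADE. The documents do not support that.

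- Section 11.7 does not mention UADEs. The full definition still stands in section 11.2, the protocol adopts the 21 CFR 812 definitions, and the duty in section 11.5 and the triggers in sections 12.1 and 12.2 all use the defined term.
- Device-related DKA, HHS and severe hypoglycemia are expedited regardless. Coma, death, shock and cardiovascular event appear in Table 4 mainly as consequences of low or high glucose, and many such cases would enter by one of those three triggers.
- Sites are to report all SAEs and SADEs as soon as possible, ideally within 24 hours. The CEC reviews them and may consider whether an event was unanticipated. The DMC tracks rates of all SAEs and of device-related AEs, which partly covers incidence, and can meet ad hoc.
- How many serious events remain possible UADEs cannot be judged without the application and the report of prior investigations.

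All of this stands and limits the point. It does not remove it. Section 11.7 is the protocol's stated test of anticipated status, the sponsor is the one applying it, and nothing tells the sponsor to return to section 11.2. The backstops are also weaker: CEC review outside the expedited list has no stated deadline, its look at anticipated status is optional, and no rule requires an ad hoc DMC meeting for these events.

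**Conclusion.** The conflict between sections 11.2 and 11.7 is real and should be resolved. It is confined to serious device-related events outside DKA, HHS and severe hypoglycemia that are already named somewhere but prove more severe or more frequent than previously identified. Such events could miss the UADE route; it does not follow that they must. The delay in DMC review is modest on average and up to about two months at worst. The larger loss is that the early FDA notice and the required DMC meeting would no longer be triggered.

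This assumes that the sponsor applies section 11.7 as written. If it already applies section 11.2 in full, practice is sound and only the text needs correcting. No endpoint, hypothesis test or sample size is affected.

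**What to change.** Reconcile section 11.7 with section 11.2 in one or two sentences:

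- For serious device-related events, UADE status is decided by the section 11.2 definition: nature, severity or degree of incidence, judged against the investigational plan or application.
- Being named in Table 4, the labeling or the user guide does not by itself make such an event anticipated.

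Non-serious device-related events can keep the present section 11.7 label. It would be a mistake to require identified nature, severity and incidence for every device-related event: Table 4 gives no incidences, so nearly all of them could become unanticipated.

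The cost is a short text change and probably a few more serious events handled as UADEs. How many depends on what incidences the application gives, which is not visible here. Visits, endpoints and analyses are unchanged.

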12.1 Clinical Events Committee

A clinical events committee (CEC) consisting of external physicians with an expertise in endocrinology and the management of diabetes including insulin pumps and CGM will be convened. The CEC will review AEs as required per protocol, which include reports of:

- Serious adverse event
- Serious adverse device effect
- Unanticipated adverse device effect
- Severe hypoglycemia
- Diabetic ketoacidosis
- Diabetic hyperglycemic hyperosmolar syndrome
- Severe hyperglycemia

CEC is to review and adjudicate unanticipated adverse device effects (UADE), device related DKA, device related HHS, and device related severe hypoglycemia within 10 business days from the time that the sponsor is notified. Adjudication will occur once all applicable documentation has been

received and reviewed by the CEC.

The CEC will assess events to determine agreement or disagreement with the investigator classification of an event.

If the CEC disagrees with the investigator's classification of the event, the rationale will be provided to the investigator. If the investigator agrees with the CEC's adjudication, the CRF documenting the AE will be updated accordingly.

If the investigator does not agree with the CEC's adjudication classification, both determinations will be provided within the final report; however, the CEC's adjudication will be used for data analysis. The disagreement will also be included in reporting to IRBs and regulatory authorities, if required.

The CEC may review applicable information for device related AEs which may include:

- Whether or not the event was unanticipated
- Review of sensor data from CareLink Personal/CareLink system software report (when applicable)
- Review of pump data from CareLink Personal/CareLink system software report (when applicable)
- Misuse of the device by the user

Review of events may require the following information. Final disposition may be delayed based on obtaining this information:

- Monitoring by sponsor at investigational center
- Device return and failure analysis
- CareLink Personal/CareLink system software upload and review of software reports
- Subject clarification to investigational center regarding details about the event
- Source documents that support event: Paramedic records; ER records; Lab records; Hospital admission and discharge summary

The following factors should be carefully considered in the CEC's recommendation to sponsor:

1. Was the severe hypoglycemia, HHS or DKA related to the AHCL algorithm, or was it related to a known insulin pump risk? For example, a question that may be considered in HHS or DKA would be whether the event was related to an infusion set issue or caused by the AHCL algorithm.
2. Another important consideration would be if the severe hypoglycemia, severe hyperglycemia, HHS or DKA event was related to a device malfunction versus patient non-compliance. For example, if a software anomaly leading to an under-delivery of insulin is discovered versus the subject repeatedly ignoring alarms prompting the subject to take action.

3. Severe hypoglycemia, severe hyperglycemia, HHS or DKA caused directly by an infusion set issue when the study pump is functioning as intended would likely result in acceptance to proceed with the study versus severe hypoglycemia, HHS or DKA that are directly caused by the AHCL algorithm or a device malfunction might stop study enrollment or entire study altogether.
4. It should be noted that the final determination of causality related to 780G system that is made by the CEC may include additional factors which the members consider to be clinically relevant and important.

12.2 Data Monitoring Committee

A data monitoring committee (DMC) consisting of external physicians with an expertise in Endocrinology and the management of insulin-requiring diabetes including CGM, along with an external statistician will be convened to review study progress and safety. The Board will convene approximately every 90 days. The Board will also meet when ad hoc review is required.

The DMC will perform 4 main functions:

First: DMC will track and trend the overall safety of the study.

Event rate, defined as number of events per 100 patient years will be reviewed by the DMC with respect to the following:

- Event rate of all SAEs
- Event rate of severe hypoglycemia
- Event rate of severe hyperglycemia
- Event rate of DKA
- Event rate of HHS
- Event rate of device related AEs

Second: Based on their meetings, DMC will recommend a decision to the sponsor regarding the following:

- Whether or not enrollment should be halted.
- Whether or not the entire study will need to be stopped including for those subjects who have received study devices already.

Note: If it is decided to withdraw subjects from participation in the study or if the study is stopped, subjects will be followed-up in accordance with standard practice by their own providers.

Third: During the study, the following steps will be taken for:

- UADE

- Device related DKA
 - Device related HHS
 - Device related Severe Hypoglycemia
1. Investigational center staff will notify the sponsor within approximately 24 hours of investigator or study coordinator awareness of events described above.
 2. Sponsor will notify the FDA within approximately 3 business days of awareness of the event and provide updates to the agency as information becomes available.
 3. DMC is to meet within 10 business days from CEC adjudication of the event. The investigator should be available to answer questions from DMC, as needed.
 4. Based on their review, DMC will recommend that the sponsor make a decision regarding the following:
 - a) Whether or not subject enrollment may continue
 - b) Whether or not new subject enrollment should be suspended, with enrolled subjects continuing in the study.
 - c) Whether or not the entire study should be stopped, including those subjects who have already received study devices.
 5. DMC and/or IRB will recommend whether or not the study should be stopped based on the number of events that have occurred during the study, weighed against the potential benefits of continuing the study.

Note: If it is decided to withdraw subjects from participation in the study or if the study is stopped, subjects will be followed-up in accordance with standard practice by their own providers.

Fourth: The DMC will provide a recommendation to proceed with the following staged enrollment:

After 10 subjects with a TDD at or below 125 units have completed 6 weeks of the study period, the DMC will assess if it is safe to proceed with subjects using SmartGuard who have a TDD of greater than 125 units.

General guidance for DMC's recommendations to sponsor should be based on the following:

In general, a DMC recommendation regarding study stoppage or resumption of enrollment should be made to the sponsor within 1 week of the DMC meeting where the determination is made. However, if more data is needed, the DMC may meet again to re-assess their decision within 2 weeks or when required data becomes available.

13. Device Deficiencies and Troubleshooting

The Medtronic 24-Hour Technical Support (TS) will be consulted for device troubleshooting (e.g., assistance is needed by subject to operate their device[s]). When subjects call the TS, they are instructed to notify the TS operator that they are currently participating in a clinical research study. All device deficiencies that are reported to the TS will be documented by the TS staff.

The investigational center will be provided with a copy of all TS calls for their subjects. The TS call reports should be reviewed for investigational center staff awareness and assessment for the possibility of an AE. If an AE is detected the investigational center staff will complete the appropriate eCRF(s).

All device deficiencies reported directly to the investigational center staff by a subject should either be reported to the TS by the subject or investigational center staff. Any device deficiency the investigational center may have should be reported to the TS.

Device Deficiency (ISO 14155:2020)

A device deficiency is any inadequacy of a medical device with respect to its identity, quality, durability, reliability, usability, safety, or performance.

Note 1 to entry: Device deficiencies include malfunctions, use errors, and inadequacy in the information supplied by the manufacturer including labeling.

Note 2 to entry: This definition includes device deficiencies related to the investigational medical device or the comparator.

To return a study device as part of a device deficiency, the investigational center staff and/ or subject are required to call the 24-Hour TS. Following the call to TS, the investigational center staff should then follow the study procedures for returning products with device deficiencies.

It is the responsibility of the investigator to follow their IRB reporting requirements.

14. Statistical Design and Methods

14.1 General Aspects of Analysis

For each phase, all data collected from the time of screening until the end of the study will be collected on eCRFs, subject questionnaires, and electronically by uploading the various devices. For each phase, data and analyses will be summarized in a Clinical Study Report. Any deviations from original statistical plan and the rationale will be described in the Clinical Study Report.

